Regaining upper extremity function is very important for stroke survivors to increase their independence and ability to perform ADLs. The large majority of outpatient stroke rehabilitation currently takes place in a therapy clinic; however, access is often limited by resource allocation, financial hardship, and transportation difficulties. The Smart Glove is unique in its portability, ease of use, and low cost. It could easily be provided to stroke patients with limited financial resources and, because of its portability, can be shipped to patients in more geographically remote areas who have limited access to regular therapy services. Thus, if successful, this research could lead to a novel rehabilitation method that provides value-based care to a large proportion of stroke patients with impaired arm function.

Study Sites

Stanford University will be the Coordinating Center for this study. Patients will be recruited from the Inpatient Stroke Unit, the Outpatient Stroke Clinic, or Stanford-affiliated Acute Rehabilitation Units. Stanford's CTRU and the Neurology Outpatient Clinic will be used for study visits and assessments. Other non-Stanford affiliated sites will be invited to participate and will require separate IRB approval per their institution. A total of 80 patients will be included.

Patient Population

Patients will be eligible for the study if they (1) have a history of an ischemic or hemorrhagic stroke and (2) have impaired arm/hand function secondary to the stroke (see below for specific inclusion and exclusion criteria). We will recruit 40 patients over a 4-year period at Stanford's acute care hospitals, acute rehabilitation units, and outpatient facilities. The doctor and/or research coordinator may introduce the study to potential candidates in-person in the aforementioned sites, and the research coordinator may contact potential candidates by phone after the doctor's referral. Enrolled patients will be randomized (1:1 ratio) to standard

rehabilitation therapy versus standard rehabilitation therapy plus Smart Glove use. All patients will be allowed to participate in any scheduled outpatient rehabilitation during the study. Patients who are randomized to the Smart Glove treatment arm will take the Smart Glove with them if they transition between facilities; for example, if they transition from the acute hospital to an acute rehabilitation facility or to home.

Inclusion Criteria:

- (1) a diagnosis of ischemic or hemorrhagic stroke

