- (2) unilateral hand/arm weakness from stroke with indication for upper limb rehabilitation therapy.
- (3) ability to successfully play 2 out 4 pre-selected test games with the Smart Glove. The test specific games and criteria for passing are as follows:
 - Pour the wine (Pronation/Supination): **make 5 pours in first 1 minute**
 - Snow Ball Fight (Wrist Flexion/Extension w/ gravity eliminated): **take down 3 objects in first 1 minute**
 - Scrub the Floor (Wrist Radial/Ulnar deviation w/ gravity eliminated): **scrub the floor 5 times in first 1 minute**
 - Float the Fish (Finger Flexion/Extension): **make 50 meters with 3 or less bumps in first 3 minutes**

Exclusion Criteria:

- (1) Age <18 years
- (2) history of visually provoked seizures.
- (3) psychological disorder that could impede participation.
- (4) pre-existing neurologic disorder which causes significant deficits in arm/hand function (e.g. Parkinson's disease, peripheral neuropathy, etc.).
- (5) severe receptive aphasia which results in inability to participate with the Smart Glove.
- (6) cognitive impairment which results in inability to participate with the Smart Glove.
- (7) severe pain impeding upper extremity rehabilitation and use of the Smart Glove.
- (8) limited life-expectancy which makes it unlikely that patient will be able to complete the 24-week follow-up visit
- (9) any medical or other condition that, in the opinion of the investigator, makes the patient unsuitable for participation in this study.

Randomization: Once the participant has given informed consent and enrolled in the study, they will be randomized in a 1:1 ratio to Smart Glove therapy plus usual care versus usual care alone. A dynamic stratification system will ensure well-balanced subgroups. The randomization algorithm will employ biased-coin minimization and the variance method with stratification weights (8). The strategy is to balance treatment assignment along the marginal distribution of each stratification factor. The stratification factors used, will be: 1) age, 2) time from symptom onset to enrollment, 3) finger extension muscle testing score at enrollment, and 4) study site.

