Jebsen Taylor Hand Test (JTHT)	X		X		X		X
Upper Extremity Fugl-Meyer (FM)	X		X		X		X
Manual Muscle Testing (MMT)	X				X		X
Stroke Impact Scale (SIS)					X		X
Assess amount of rehabilitation			X		X		X
User Survey (Smart Glove arm)					X		

Data analyses: All efficacy analyses are analyzed under the intention to treat principle. The primary efficacy outcome is the change in score on the Jebsen Taylor Hand Test between baseline and week 12. Secondary efficacy endpoints are changes in scores on the upper extremity Fugl-Meyer Scale, modified Rankin Score, total NIHSS score, Manual Muscle testing (of the biceps, triceps, wrist extensors, finger flexors, and finger abductors), Stroke Impact Scale, and total dose of rehabilitation received during the 12-week intervention period. Persistence of the treatment effect will be tested by comparing changes in scores on the Jebsen Taylor Hand Test and Fugl-Meyer upper extremity score at 24 weeks between treatment groups. Differences between treatment groups will be assessed using a generalized linear model (GLM) that accounts for repeated measures (assessments at baseline, 6 and 12 weeks for primary outcome, as well as 24 weeks for secondary outcome) and will be adjusted for imbalances in baseline variables. We will use a two-sided test with an alpha of 0.05 to declare significance. Based on prior studies we assume to see an 11.0-point improvement on the JTHF

test in patients who use the glove, a 3.0-point improvement in control subjects, and a standard deviation of the change score of 2.0.(1) Based on these assumptions we will have more than 90% power to show a significant effect of the use of the Smart Glove on our primary efficacy outcome.

Risks

Potential risks and inconveniences include that the participant will need to travel to Stanford for 3 follow-up visits over the course of the study. One may also experience technical difficulties in using the Smart Glove system. There is a low likelihood of one having a skin reaction to the material used to make the Smart Glove.

Benefits

While there is no definitive evidence that SmartGlove therapy will benefit patients, a potential benefit is that the participant may experience improvement in the function of their affected upper extremity as a result of study participation.

Withdrawal

Each subject and the investigator reserve the right at any time to terminate a subject's participation in the clinical investigation. Possible reasons for study withdrawal:

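### The only covariate rule for the primary model is adjustment for observed imbalances; a fixed list of baseline JTHT plus the four minimization factors would be a cheap improvement

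*Combined protocol and SAP*

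**What the plan says.** All of the analysis plan is in the Data analyses section of the combined protocol and SAP.

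- Endpoint: "The primary efficacy outcome is the change in score on the Jebsen Taylor Hand Test between baseline and week 12".
- Model: a generalized linear model that "accounts for repeated measures (assessments at baseline, 6 and 12 weeks for primary outcome, as well as 24 weeks for secondary outcome".
- Covariates: the model's results "and will be adjusted for imbalances in baseline variables". No variable is listed and no criterion for imbalance is given, here or elsewhere.
- Power inputs: improvements of 11.0 and 3.0 points in the two arms, and "a standard deviation of the change score of 2.0".

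The Randomization section uses biased-coin minimization. "The strategy is to balance treatment assignment along the marginal distribution of each stratification factor". The factors are age, "time from symptom onset to enrollment, 3) finger extension muscle testing score at enrollment, and 4) study site". Baseline JTHT is not among them, but it is measured at the Day 0 visit (Table 1).

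On size, Study Sites says "A total of 80 patients will be included", and Patient Population says of the Stanford facilities "We will recruit 40 patients over a 4-year period".

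**The concern.** A rule triggered by imbalance chooses covariates for the wrong reason. A covariate earns its place in a randomized comparison because it predicts the outcome, whether or not the arms happen to differ on it. This wording has three consequences.

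1. The covariate set cannot be known until baseline data are in, and it then rests on an unstated criterion.
2. Nothing commits the analysis to baseline JTHT, a natural candidate to predict week-12 JTHT. Listing baseline among the repeated assessments does not do this job: with free baseline means in each arm and complete data, the week-12-minus-baseline contrast is no more precise than a plain comparison of change scores.
3. The rule points away from the four minimization factors. Minimization makes them look balanced, so they would usually be left out. Yet when allocation has been balanced on prognostic factors, an analysis that ignores them overstates its standard error.

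What is at stake is precision, and a test that holds its nominal level rather than falling below it. False positives are not the issue.

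**Working it through.** **Inputs.** From the documents: SD of change 2.0, difference 11.0 - 3.0 = 8.0 points, two-sided alpha 0.05, 1:1 allocation, 80 patients in total and 40 at Stanford (so n = 40 or 20 per arm). Assumed, because the documents do not give them: the baseline to week-12 correlation rho (0.5, 0.7, 0.9), equal variances at the two visits, normal and complete data, and for minimization four independent binary factors, equal weights and a coin of 0.8.

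**The plan's own figure.** The SE of the difference in change is 2.0 × sqrt(2/n), which is 0.447 at 40 per arm and 0.632 at 20. The ratios 8/0.447 = 17.9 and 8/0.632 = 12.6 give power of about 100% in both cases, consistent with the stated figure of more than 90%. The points below do not alter it.

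**Change-score reference.** The 95% half-width is t × SE: 1.991 × 0.447 = 0.89 points (40 per arm) and 2.024 × 0.632 = 1.28 points (20 per arm).

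**Adding baseline JTHT.** The average variance ratio, adjusted to change score, is (1 + rho)/2 × (1 + 1/(2n - 4)). For example, at rho 0.5 and n = 40 it is 0.75 × (1 + 1/76) = 0.76. Holding the SD of change at 2.0 ties each rho to a visit SD of 2.0/sqrt(2(1 - rho)).

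| rho | Implied visit SD | Variance ratio, 40 / 20 per arm | Half-width, 40 / 20 per arm | Trials with a wider interval, 40 / 20 per arm |
|---|---|---|---|---|
| 0.5 | 2.0 | 0.76 / 0.77 | 0.78 / 1.13 | 0.2% / 4% |
| 0.7 | 2.6 | 0.86 / 0.87 | 0.83 / 1.20 | 2% / 15% |
| 0.9 | 4.5 | 0.96 / 0.98 | 0.87 / 1.27 | 27% / 48% |

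The last column comes from a null simulation of 100,000 trials per setting, whose variance ratios agree with the formula to within 0.003. Setting the ratio to 1 gives the break-even: 2/(1 + 1/76) - 1 = 0.974 at 40 per arm and 2/(1 + 1/36) - 1 = 0.946 at 20. The implied visit SDs there are about 8.8 and 6.1 points.

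**Leaving out the minimization factors.** Let the factors explain a share R² of the change variance. If balance were perfect, the true variance would be (1 - R²) times what the unadjusted test assumes, so its size would be about 2 × [1 - Φ(1.96/sqrt(1 - R²))]. That is 3.9% for R² = 10% and 2.4% for 25%. Biased-coin minimization balances imperfectly, so the simulated values lie slightly higher (100,000 trials per setting).

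| R² | Type I error without / with factors, 40 per arm | Half-width without / with, 40 per arm | Type I error without / with, 20 per arm | Half-width without / with, 20 per arm |
|---|---|---|---|---|
| 0% | 5.1% / 5.0% | 0.887 / 0.891 | 5.0% / 5.1% | 1.273 / 1.293 |
| 10% | 4.1% / 5.1% | 0.888 / 0.845 | 4.2% / 5.0% | 1.274 / 1.226 |
| 25% | 2.7% / 5.0% | 0.889 / 0.772 | 2.9% / 5.0% | 1.276 / 1.120 |

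If the factors explain nothing, including them costs 0.891 - 0.887 = 0.004 points of half-width at 40 per arm and 1.293 - 1.273 = 0.02 at 20.

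**Does an imbalance trigger inflate error?** One explicit version was simulated at 40 per arm: adjust for baseline JTHT only if the arms differ on it at p<0.05, and otherwise compare change scores. Type I error was 4.3%, 4.7% and 4.9% at rho 0.5, 0.7 and 0.9.

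**The case against.** The strongest reply is that little is broken. The endpoint, time point, visits, alpha and sidedness are all fixed; baseline JTHT is in the model as a repeated assessment; and no stated figure changes. All of that stands.

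The precision gain can also be questioned. Gains of 24% and 14% need a between-patient JTHT SD of only 2.0 to 2.6 points, in a plan that assumes an 11-point mean improvement and, beyond passing two of four test games, sets no limit on stroke severity. If patients vary more than that while the SD of change stays at 2.0, the correlation is higher and the gain smaller; beyond the break-even there is none on average. This stands as a limit on size. The documents give no visit SD, so it cannot be settled from them.

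For the minimization factors, the levels, weights, coin and explained variance are all assumed, and an unstated number of sites could use more degrees of freedom than a binary factor. This too stands. It does not rescue the rule, which would tend to omit these factors however prognostic they are.

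A reader might go further and infer two things that the documents do not support.

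- *That the week-12 test is not fixed in advance.* The endpoint definition names week 12, and the between-arm contrast at week 12 is its natural and valid reading. A sentence naming that contrast as the primary test would be helpful detail; its absence does not leave the time point open.
- *That type I error is inflated.* Taking the better of a change-score test and a baseline-adjusted test would give 7.3%, 6.9% and 6.0% at 40 per arm for the three correlations. The plan grants no such choice: it describes adjustment in response to imbalance, and the rule of that kind that was tested stays below 5%.

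**Conclusion.** The point holds as a cheap improvement. The covariate rule depends on the data, does not commit to baseline JTHT, and would usually omit the factors used in the allocation.

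The firmer part is the minimization factors: if they are prognostic, leaving them out gives a conservative test and an interval that is too wide, by 0.89 - 0.85 = 0.04 or 0.89 - 0.77 = 0.12 points of half-width at 40 per arm for the two assumed shares. The gain from baseline JTHT may be useful or negligible, depending on a correlation that the documents do not give.

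All these amounts are small beside the assumed 8-point effect. They would matter more if the true effect were smaller or the SD larger than planned. Validity and stated power are not affected.

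**What to change.** In the Data analyses section, replace the imbalance wording with a list settled before outcomes are compared by arm:

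- baseline JTHT, either as a covariate or as a response with the arm means constrained equal at baseline, but not both;
- age, time from onset, finger extension score and site (site drops out if only one site enrolls; small sites can be pooled).

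Add a sentence naming the treatment contrast at week 12 as the primary test. The endpoint can stay as change from baseline: once baseline is a covariate in a week-12 comparison, change and week-12 score give the same treatment estimate.

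The cost is two or three sentences, with no new data, visits or patients. The statistical price is one degree of freedom for baseline JTHT plus those for the four factors, more if many sites enroll. The interval will also be slightly wider in some trials if the baseline to week-12 correlation is about 0.9 or higher.

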While these preliminary studies show promising results, important questions remain unanswered. These include: Can patients use self-guided Smart Glove therapy in their home or rehabilitation environment in addition to their routine rehabilitation therapy in the sub-acute

stroke period? Is the addition of Smart Glove therapy to routine rehabilitation therapy beneficial for recovery of arm and hand function? We will address these questions in the vREHAB study.

Primary Hypothesis

Our hypothesis is that self-directed use of the Smart Glove is feasible for subacute as well as chronic stroke patients, results in an increased dose of upper extremity rehabilitation, and leads to improved functional outcome and quality of life for stroke survivors.

Specific Aims

Aim 1: Demonstrate the feasibility of increasing the dose of rehabilitation in acute stroke patients with the Smart Glove. We hypothesize that patients randomized to the Smart Glove will have more upper extremity therapy than patients randomized to standard of care therapy.

Aim 2: Demonstrate the effect of Smart Glove use on functional recovery. We hypothesize that patients randomized to Smart Glove will have a greater improvement in arm/hand function as assessed on the Jebsen Taylor Hand Function (primary efficacy outcome) and Fugl-Meyer tests at the end of the intervention period, and that this improvement is sustained 12 weeks after completion of the intervention.

Aim 3: Demonstrate the effect of Smart Glove use on quality of life. We hypothesize that, compared to controls, patients randomized to Smart Glove will have a greater improvement in self-rated stroke related disability and quality of life (assessed with the Stroke Impact Scale) at the end of the intervention period, and that this improvement is sustained 12 weeks after completion of the intervention.

Relevance

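### The 0.05 rule is not limited to the primary test, and nothing orders, gates or labels as supportive the other efficacy tests behind Aims 2 and 3

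*Combined protocol and SAP*

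**What the plan says.** All of the analysis text is in the Data analyses section of the combined protocol and SAP.

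- **Primary:** "The primary efficacy outcome is the change in score on the Jebsen Taylor Hand Test between baseline and week 12".
- **Secondary:** "Secondary efficacy endpoints are changes in scores on the upper extremity Fugl-Meyer Scale, modified Rankin Score, total NIHSS score", then "Manual Muscle testing (of the biceps, triceps, wrist extensors, finger flexors, and finger abductors"), then "Stroke Impact Scale, and total dose of rehabilitation received during the 12-week intervention period".
- **Week 24:** "Persistence of the treatment effect will be tested by comparing changes in scores on the Jebsen Taylor Hand Test and Fugl-Meyer upper extremity score" between the arms.
- **Model:** one repeated-measures generalized linear model is assigned to differences between the arms, with visits named for both the primary and the secondary outcome.
- **Decision rule:** the next sentence is "We will use a two-sided test with an alpha of 0.05 to declare significance". The power statement, which concerns the primary outcome only, follows it.

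Under Specific Aims, each of the three aims opens with the verb 'Demonstrate'. Aim 2 covers JTHT (labelled there as the primary efficacy outcome) and Fugl-Meyer (FM), with persistence 12 weeks after the intervention. Aim 3 reads "Aim 3: Demonstrate the effect of Smart Glove use on quality of life". It is assessed with SIS only, at the end of the intervention and again 12 weeks later. Aim 1 concerns feasibility and rehabilitation dose.

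The document contains no multiplicity adjustment, no testing order among the non-primary endpoints, no condition that the primary succeed first, and no statement that the other results are supportive or exploratory.

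**The concern.** The labels 'primary' and 'secondary' are the only ranking in the plan, and no decision rule is attached to them. As written, if the JTHT comparison at week 12 is not significant, a nominal p-value below 0.05 on FM, SIS or a week-24 comparison could still be declared significant and reported as meeting an aim. Aim 3 is the clearest case, because its only endpoint is a secondary one.

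At stake is how the secondary and persistence results may be worded in the trial report. With several such tests and no true effect on any of them, a chance finding in favour of the glove is more likely than the 2.5% that a single two-sided 0.05 test allows in that direction.

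**Working it through.** **1. The plan's own figure.** The documents state no familywise error rate. The only stated operating figure is power above 90% for the primary. Inputs from Data analyses: improvements of 11.0 and 3.0 points (difference 8.0), SD of change 2.0, two-sided 0.05. Study Sites gives 80 patients and allocation is 1:1, so 40 per arm. The noncentrality is 8.0 / (2.0 × √(2/40)) = 17.9, and power exceeds 99.99%. With 20 per arm (the 40 patients mentioned under Patient Population) it is 8.0 / (2.0 × √(2/20)) = 12.6, and power again exceeds 99.99%. The stated bound is met under the plan's assumptions and does not depend on what follows.

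**2. Counting the non-primary efficacy tests.**

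- Data analyses lists six secondary endpoints and two persistence tests, so eight in all.
- NIHSS is removed: the visit lists and Table 1 schedule it at baseline only, so its change cannot be tested.
- Rehabilitation dose is removed: it measures delivery of the intervention.
- Six remain: FM, modified Rankin Scale (mRS), manual muscle testing (MMT), SIS, JTHT at week 24 and FM at week 24. SIS has no scheduled baseline, so its change cannot be computed, but the arms can be compared at follow-up.
- If the five named muscles were tested separately there would be 6 − 1 + 5 = 10. The plan does not say that they are.
- SIS at week 24, hypothesised under Aim 3, is not in this count. It would make seven.

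**3. Independent tests, all null.**

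- Either direction: 1 − 0.95^6 = 0.265; 1 − 0.95^10 = 0.401.
- Favouring the glove (2.5% per test): 1 − 0.975^6 = 0.141; 1 − 0.975^10 = 0.224.

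**4. Correlated tests.** The documents give no correlations, so equicorrelated normal test statistics were simulated with no true effect, using Z = √r × (shared term) + √(1 − r) × (own term) and a cut-off of 1.96.

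| Tests | Correlation r | Either direction | Favouring the glove |
|---|---|---|---|
| 6 | 0 | 26.5% | 14.1% |
| 6 | 0.5 | 20.7% | 10.4% |
| 6 | 0.7 | 16.4% | 8.2% |
| 10 | 0 | 40.1% | 22.4% |
| 10 | 0.5 | 28.7% | 14.4% |
| 10 | 0.7 | 21.3% | 10.6% |

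**5. Given that the primary is not significant.** For six tests, the chance of at least one false result favouring the glove is 14% at r = 0, 9% at r = 0.5 and 7% at r = 0.7. Positive correlation lowers it, because a null primary result makes a chance excess elsewhere less likely.

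**The case against.** The strongest case for leaving the text alone has four parts.

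- **The rule may be meant for the primary only.** The alpha sentence stands directly before a power statement about the primary, so this is a possible reading. But the sentence does not limit itself, and it follows directly on a model sentence that covers both primary and secondary outcomes. If the narrow reading is intended, Aim 3 has no decision rule at all. Either way a sentence is needed.
- **This is a phase 2 trial with one labelled primary.** Unadjusted secondary endpoints are common at this stage, and a formal gatekeeping scheme would be debatable. This stands, and is why a testing hierarchy is only optional below. It does not settle the wording, because the plan itself speaks of declaring significance and demonstrating effects.
- **Persistence presupposes a week-12 effect.** On that view the two week-24 tests are not separate routes to a claim. Four tests would remain, giving 1 − 0.95^4 = 18.5% in either direction or 1 − 0.975^4 = 9.6% favouring the glove, if independent. The reading is reasonable, but no condition to that effect is written.
- **Independence is implausible** for hand and arm measures on the same limb, some of them repeated. This also stands, and the lower ends of the ranges are there for that reason.

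A reader might infer a 20-40% chance of a false efficacy claim. The documents do not support that. Figures of that size count significance in either direction, including results against the glove. The 40% also needs ten independent tests, and so a muscle-by-muscle analysis that the plan does not state.

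**Conclusion.** The gap is real but limited. The plan does not say which results may be declared significant beyond the primary, while Aims 2 and 3 are worded as if several may be.

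- **Six tests:** about 16-26% for at least one false significant result in either direction, about 8-14% favouring the glove, and about 7-14% favouring the glove given that the primary fails.
- **Ten tests, only if muscles are analysed separately:** 21-40% in either direction and 11-22% favouring the glove.

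These figures rest on three assumptions: no true effect on any non-primary endpoint, a common correlation between 0.7 and 0, and the test count above.

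A reader might also infer that the trial's main conclusion is compromised. It is not: there is a single primary test, its 5% error is not inflated, and its stated power is unchanged. Nor do all three aims contribute. Aim 1 concerns feasibility and dose, so only Aims 2 and 3 supply efficacy tests. What is affected is the strength of language that the secondary and persistence results can bear.

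**What to change.** In Data analyses, state that significance is declared at two-sided 0.05 only for the change in JTHT at week 12. State that all other efficacy endpoints (FM, mRS, MMT, SIS at weeks 12 and 24, and JTHT and FM at week 24) are reported as supportive estimates with 95% confidence intervals and no declaration of significance. Word the Aim 3 and persistence conclusions to match. Report rehabilitation dose separately, as delivery of the intervention.

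A prespecified fixed sequence after the primary, each step at 0.05 and stopping at the first failure, is an optional alternative. If it is used, SIS at week 24 must either have a place in the sequence or be listed as estimate-only. SIS must also be compared between arms at follow-up rather than as a change, because no baseline SIS is scheduled.

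The cost is wording only: no patients, no visits and no loss of power for the primary. The downside is that Aim 3 and persistence can no longer be claimed as statistically demonstrated on a nominal p-value alone. Under the fixed sequence, an endpoint low in the order cannot be claimed if one above it fails.
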